Comparing Intubation rates in the delivery room by interface

NCT05609773

July 19, 2022

Research Proposal Department of Pediatrics

Project Title: Comparing intubation rates in the delivery room by interface

7-19-2022

Study Personnel:

Name, degree	Role	Employer
[name]	Co-PI	UICOMP
[name]	Co-PI	UICOMP
M. [name]	Investigator	UICOMP
[name]	Mentor	UICOMP
[name]	Collaborator	UICOMP

Study Sites:

OSF - St. Francis Medical Center - Peoria St. Jude Midwest Affiliate

Unity Point Methodist/Proctor UICOMP

Other:

Anticipated study duration after start: 1 year

Needed services:

Statistician Healthcare Analytics

Funding source:

The research specified in this protocol will not be funded.

The research specified in this protocol is funded by a pharmaceutical/device company.

The research specified in this protocol is funded through NIH

- Other: applying for department and CHOI grant funding
- This study has been reviewed with the relevant division(s) or division head(s).
- I request detailed feedback/mentorship from the Research Facilitation Committee for this project.

Background and rationale

Although the majority of premature neonates < 30 weeks gestation require positive pressure ventilation (PPV) at birth, the optimal interface to provide PPV has not been determined. Preferably this support would be provided by non-invasive means to prevent the development of bronchopulmonary dysplasia. Resuscitation with a face mask, single nasal tube, nasal prongs, and/or LMA are all approved methods of resuscitation per NRP as of 2010. Face masks have been associated with more dead space, air leak and airway obstruction however are the most commonly used interface. Recently, the Trigeminal Cardiac Reflex has been described, which can be induced with the placement of a facemask, resulting in bradycardia and apnea. Bi-nasal prongs (RAM cannula) have been found in studies to be associated with lower intubation rates in the delivery room (down to 24 weeks gestation), less need for epinephrine, chest compressions, and subsequent invasive ventilation. In addition to the potential practical advantages of bi-nasal prong resuscitation, there is evidence to suggest that ventilation through the nose may stimulate the subepithelial receptors of the upper airways causing an increase in respiratory rate and depth.

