Both binasal prongs and face masks are acceptable by NRP and have been utilized for neonatal resuscitation at OSF SFMC since 2016, however the choice is by provider preference with rare use of the bi-nasal prongs. Also, historically we have provided constant positive airway pressure (CPAP) during delayed cord clamping with a facemask by the OB team who needs to remain sterile during a C/S (majority of premature deliveries). Thus, nearly all babies have had some exposure to a facemask during the initial resuscitation period.

For our prospective study we will sterilize facemasks, bi-nasal prongs, and tubing. A neonatal provider will scrub and don sterile gown and gloves to be able to provide the infant with the CPAP utilizing the study interface during delayed cord clamping. That same interface will be continued during resuscitation measures after delayed cord clamping is complete.

The interface utilized in the delivery room to provide resuscitation has been recorded in the Vermont Oxford Database since 2018. On retrospective review of patients born < 30 weeks' gestation, 7/30 of neonates resuscitated with bi-nasal prongs were intubated in the delivery room (23%) and 114/136 of neonates resuscitated with facemask were intubated in the delivery room (84%). There were 33 infants in which both a facemask and bi-nasal prongs were utilized during initial resuscitation as well, 13 of required intubation (39%). However, we are unable to determine from the database which interface was utilized first. Also, prior to 2021, only one neonatologist was utilizing bi-nasal prongs thus it is difficult to determine if the difference is entirely due to the interface alone.

Specific Aims/Objectives

We hypothesize that there will be at least a 40% reduction in the rate of intubation for patients born < 30 weeks' gestation when bi-nasal prongs are utilized for neonatal resuscitation vs face mask.

Research Design and Methods

1. Subject population

Subject identification/recruitment:

All patients born at OSF SFMC < 30 weeks' gestation

Inclusion/exclusion criteria, including age:

Inclusion: all resuscitated infants < 30 weeks' gestation born at OSF SFMC

Exclusion: diagnosis of congenital diaphragmatic hernia, no PPV needed, or no resuscitation desired due to major congenital anomalies or peri-viable status

Estimated sample size:

Hypothesis: 40% reduction in intubations in the delivery room

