Baseline intubation rate for facemask resuscitation in neonates < 30 weeks from 2018-2020: ~80% (retrospective intubation rate for ram cannula resuscitation 23%)

alpha 0.05, beta 80%

Estimated sample size = 42 patients

Estimated M:F ratio:

1:1

2. Study design (specify study type, any randomization or control groups)

Prospective stratified randomization with separate blocks for neonates with a gestational age < 25 0/7 weeks and those 25 1/7 weeks to 29 6/7 weeks gestation.

3. Procedures (step by step description of each part of the study, tools to be used, any subject compensation)

- 1) Consent would be obtained prior to birth by neonatologist
- 2) Randomization would occur prior to delivery
- 3) Patients receiving non-randomized apparatus will be considered a protocol violation.
- 4) CPAP will be set up prior to either c/s or vaginal delivery utilizing either an appropriately sized face mask or ram cannula. Sterile packets with tubing and prongs or a facemask will be supplied for C/S.

a) Bi-nasal prong Resuscitation

- i) Settings on T-piece are set to PIP of 22, PEEP of 6, Flow of 10 L, FiO₂ 30%. (Settings are slightly higher than facemask to account for known leak with RAM cannula so the pressure seen by the lungs should be equivalent between the nasal prongs and facemask.)
- ii) Immediately after delivery, place the RAM cannula in correct position with the prongs in the nares (prongs should face down into the nasopharynx) and tighten the strap around the head.
- iii) If the neonate is actively breathing, provide CPAP via the RAM cannula and T piece
- iv) If the neonate is apneic or ineffectively breathing, provide PPV via the RAM cannula and T piece at a rate of 40-60 breaths per minute by holding the cannula with your thumb and closing the mouth with your middle finger to ensure a proper seal
- v) If the heart rate starts to increase, continue with resuscitation per NRP guidelines
- vi) If the heart rate does not increase appropriately, troubleshoot the RAM cannula:
 - (1) Suction nares and mouth
 - (2) Maintain Closed mouth
 - (3) Adjust RAM Cannula in nose to ensure seal
 - (4) Reposition head and neck to open airway
 - (5) Increase pressure by increments of 2 until adequate chest rise is seen or at a PIP of 30
 - (6) Alternative Airway (intubation)

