- vii) When 60 seconds of delayed cord clamping is complete (if appropriate to perform delayed cord clamping) - Patient will move on the bed to the resuscitation room to complete resuscitation as above. Pulse oximeter to be placed on the right wrist and EKG leads placed in the appropriate position.

a. Face mask resuscitation

- i. Settings on T-piece are set to PIP of 20, PEEP of 5, Flow of 10 L, FiO₂ 30%.
- ii. After delivery, place the face mask in the correct position on the face, bringing the chin to the mask

- iii. If the neonate is actively breathing, provide CPAP via the Face Mask and T piece
- iv. If the neonate is apneic or ineffectively breathing, provide PPV via the Face Mask and T piece at a rate of 40-60 breaths per minute
- v. If the heart rate starts to increase, continue with resuscitation per NRP guidelines
- vi. If the heart rate does not increase appropriately, troubleshoot the Face Mask:
 - 1. Adjust the Face Mask
 - 2. Reposition the head and neck to open airway
 - 3. Suction mouth, then nares
 - 4. Open Mouth
 - 5. Increase pressure by increments of 2 until adequate chest rise is seen or at a PIP of 30
 - 6. Alternative airway (intubation)
- vii. When 60 seconds of delayed cord clamping is complete (if appropriate to perform delayed cord clamping) - Patient will move on the bed to the resuscitation room to complete resuscitation as above. Pulse oximeter to be placed on the right wrist and EKG leads placed in the appropriate position.

4. Statistical Analysis Plan (sample size, power justification, specific tests to compare variables)

Primary objective: 40% reduction in intubation rate from resuscitation with facemask vs binasal prongs.

Secondary objectives: incidence of chest compressions and epinephrine in the delivery room, incidence of chronic lung disease, mortality, severe IVH (grade 3-4), severe ROP (stage 3-5) - all would be compared with chi-square testing. Would also analyze average hematocrit and base deficit (if a blood gas is obtained) after admission to the NICU and compare groups via student t-test.

5. Consent procedures (if applicable, or rationale for waiver of consent; list study personnel responsible for consent)

Parents would be consented prior to birth. If parents do not consent for inclusion in the study, the neonate would be resuscitated per routine by NRP guidelines utilizing the interface of provider preference.

6. Risks to subjects/Minimization of Risks (including alternatives to treatment, and

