any benefits to participation)

Patients would have minimal risk. Both interfaces are acceptable for use by NRP. Thus, only risk would be in regards to the storage of patient information.

7. Measurement

Data to be collected:

See excel spreadsheet attached

List any additional data elements that will need to be accessed for the study, but not collected (eg when selecting patients from the EMR): None

If specimens/sample will be obtained, described how they will be labelled including any patient identifiers: N/A

8. Data Storage Plan (where/how will data be stored, accessed, and protected; paper records vs Excel/REDCap)

Data will be stored on REDCap

Duration of data storage after study completion: 3 years

Plan for deletion of data or removal of identifiers: Patient ID will be removed once all data is collected and finalized

9. Alignment (How does this project align with or add value to department/institutional objectives?)

The project is well aligned with multiple division goals - reducing intubation rates in the delivery room has the potential of avoiding CPR, allowing for LISA administration which has been associated with lower rates of severe IVH and chronic lung disease than other modes of surfactant administration. The project would also contribute significantly to the literature regarding the optimal interface device in the delivery room.

10. Goals for Publication/Presentation of Results (include plans for authorship, guidelines can be found [here](#))

Will plan to publish results and present at conferences such as PAS and AAP.

References

Aziz, Khalid, et al. "Part 5: Neonatal Resuscitation 2020 American Heart Association Guidelines for Cardiopulmonary Resuscitation and Emergency Cardiovascular Care." *Pediatrics*, vol. 147, no. Supplement 1, 2020, doi:10.1542/peds.2020-038505e.

Biniwale, Manoj, and Fiona Wertheimer. "Decrease in Delivery Room Intubation Rates after Use of Nasal Intermittent Positive Pressure Ventilation in the Delivery Room for Resuscitation of Very Low Birth Weight Infants." *Resuscitation*, vol. 116, 2017, pp. 33–38., doi:10.1016/j.resuscitation.2017.05.004.

Capasso, Letizia, et al. "A Randomized Trial Comparing Oxygen Delivery on Intermittent Positive Pressure with Nasal Cannulae versus Facial Mask in Neonatal Primary Resuscitation." *Acta Paediatrica*, vol. 94, no. 2, 2007, pp. 197–200., doi:10.1111/j.1651-2227.2005.tb01890.x.

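### Chronic lung disease and death are tested only separately, so if deaths differ between arms, the arm with more deaths can look better on chronic lung disease

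*Protocol*

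**What the plan says.** The secondary objectives in section 4 of the protocol (Statistical Analysis Plan) fix both the outcomes and the test: "incidence of chronic lung disease, mortality, severe IVH (grade 3-4), severe ROP (stage 3-5) - all would be compared with chi-square testing". Each outcome is its own two-arm comparison, and none counts death together with CLD.

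Three other places bear on the point:

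- **Weight of CLD.** Background and rationale gives lung disease as the reason for avoiding invasive support: "Preferably this support would be provided by non-invasive means to prevent the development of bronchopulmonary dysplasia". Section 9 (Alignment) mentions "LISA administration which has been associated with lower rates of severe IVH and chronic lung disease than other modes of surfactant administration" as a hoped-for gain. That sentence compares modes of giving surfactant, so its link to the interface is indirect.
- **Population.** Section 2 (Study design) describes "separate blocks for neonates with a gestational age < 25 0/7 weeks", so very immature infants are enrolled. Section 1 (Subject population) excludes cases with "no resuscitation desired due to major congenital anomalies or peri-viable status", which removes some infants at high risk of death.
- **Size.** The protocol states "Estimated sample size = 42 patients".

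**The concern.** Death before assessment removes an infant from the pool of possible CLD cases. A CLD comparison that does not count death therefore partly measures survival, and in the wrong direction: more deaths leave fewer infants who can be diagnosed.

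Choosing a denominator does not remove this. Over all randomised infants, the arm with more deaths has a lower expected CLD proportion even when survivors in both arms have the same CLD risk. Over survivors only, the groups compared are no longer those that were randomised, and the arm with more deaths gains if its deaths fell on the infants most likely to develop CLD.

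At stake is the direction in which a secondary result is read. Lung disease is part of the stated rationale, so a lower CLD count in one arm is likely to be taken as support for that interface, even if it only reflects more deaths there.

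**Working it through.** **Inputs.** From the protocol: 42 infants, and CLD and mortality as separate chi-square tests. It gives no mortality or CLD rate and no allocation ratio, so every rate below is an assumption, as is an equal split of 21 per arm.

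**Is 42 a total?** The unpooled two-sided formula for 80% vs 40% intubation at 5% alpha and 80% power gives (1.960 + 0.842)² × (0.8×0.2 + 0.4×0.6) / 0.4² = 19.6, so 20 per arm and 40 in all. That is within 2 of the stated 42, so 42 is read as the total. It concerns the primary endpoint only.

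**All randomised infants as denominator.** Let p be the CLD risk in survivors, the same in both arms, and d1 and d2 the death risks, with D = d2 − d1.

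- CLD proportion = (1 − d)p, so the arm with more deaths is lower by pD.
- Death or CLD = d + (1 − d)p, so the arm with more deaths is higher by (1 − p)D.

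| p | Deaths | CLD | Shift in CLD | Death or CLD | Shift in death or CLD |
|---|---|---|---|---|---|
| 30% | 10% vs 15% | 27.0% vs 25.5% | −1.5 | 37.0% vs 40.5% | +3.5 |
| 30% | 10% vs 20% | 27.0% vs 24.0% | −3.0 | 37.0% vs 44.0% | +7.0 |
| 30% | 15% vs 35% | 25.5% vs 19.5% | −6.0 | 40.5% vs 54.5% | +14.0 |
| 50% | 10% vs 15% | 45.0% vs 42.5% | −2.5 | 55.0% vs 57.5% | +2.5 |
| 50% | 10% vs 20% | 45.0% vs 40.0% | −5.0 | 55.0% vs 60.0% | +5.0 |
| 50% | 15% vs 35% | 42.5% vs 32.5% | −10.0 | 57.5% vs 67.5% | +10.0 |

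In infants at 21 per arm, 10% vs 20% gives 21 × 0.03 = 0.63 to 21 × 0.05 = 1.05. For 10% vs 15% it is 0.3 to 0.5, and for 15% vs 35% it is 1.3 to 2.1. With D = 0 the shift is zero.

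**Survivors only.** Assume 40% of infants are high-risk (CLD 80%) and the rest have CLD 30%, with a share s of deaths in the high-risk group. Survivor CLD = [0.8(0.4 − sd) + 0.3(0.6 − (1 − s)d)] / (1 − d).

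- s = 0.60, deaths 10% vs 20%: 0.44/0.90 = 48.9% vs 0.38/0.80 = 47.5%, a shift of 1.4 points.
- s = 0.75, same deaths: 48.1% vs 45.6%, about 2.4 points.
- s = 0.40 (deaths unrelated to CLD risk): no shift.

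**Effect on a trial of 21 per arm** (exact binomial, all randomised, uncorrected chi-square, deaths 10% vs 20%, p = 30% and 50%):

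- CLD favours the arm with more deaths in 51.9% and 56.9% of trials, against 43.0% and 43.8% if the CLD proportions were equal.
- Death or CLD favours that arm in 26.7% and 31.4%.
- The CLD test gives p < 0.05 in 6.0% of trials at either p, against 5.4% and 4.8% under equal proportions.
- The mortality test reaches p < 0.05 in 14.5%.

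**Chance imbalance.** With equal true mortality of 10%, 15% or 20%, observed deaths still differ by two or more in 42.9%, 51.1% or 56.0% of trials. In those trials CLD favours the arm with more deaths in 54-64% and death or CLD does so in 17-28%. This is chance, not bias, but it can still be misread.

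**Severe ROP.** Assuming 5-15% of survivors and D of 10 to 20 points, the shift is 21 × 0.05 × 0.10 = 0.1 to 21 × 0.15 × 0.20 = 0.6 infants per arm.

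**The case against.** **The composite does not correct the CLD comparison.** This is right. With no CLD effect in survivors, death or CLD still moves by (1 − p)D, which exceeds pD whenever p is below 50%: 7 points against 3 at p = 30% and deaths of 10% vs 20%. A reader might infer that the composite should replace CLD for inference on lung disease. The arithmetic does not support that. The composite answers a different question, about net outcome.

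**Mortality is already in the list.** An imbalance will therefore be visible, which is a real safeguard. It shows the imbalance without adjusting the CLD row, and with so few infants the mortality test will usually be non-significant even when true mortality differs.

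**A separate analysis plan may deal with it.** Denominators and definitions can properly be left there, and their absence is not the complaint. The protocol itself fixes separate tests of CLD and death, and neither usual denominator removes the problem.

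**The effect is small and rests on assumed rates.** This also stands. A reader might infer that the interfaces are expected to differ in mortality, or that a false significant CLD result is likely. The protocol gives no reason to expect a mortality difference. At 10% vs 15% deaths the CLD test rejects in 5.0-5.6% of trials, essentially the nominal rate. The larger shifts need gaps such as 15% vs 35%.

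**Severe ROP shares the mechanism.** It does, but a shift well under one infant per arm does not justify a second composite.

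**Conclusion.** The point holds in a limited, conditional form. If deaths before CLD assessment differ between arms, the CLD row as planned can favour the arm with more deaths. Over all randomised infants this follows from any difference in deaths, given equal CLD risk in survivors. Among survivors it also requires deaths to be concentrated in infants at higher CLD risk. Under the central assumption (deaths 10% vs 20%, CLD in 30-50% of survivors, 21 per arm) the size is about one infant per arm or less.

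The risk is a misread direction on one secondary outcome. Nothing here touches delivery-room intubation or the 42. It is a cheap improvement of minor severity, held with medium confidence because every rate is assumed.

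**What to change.** In section 4, add one pre-specified secondary comparison: death before CLD assessment or CLD, by randomised arm, with deaths counted as events. Report it beside the planned CLD and mortality rows, and keep both as separate components. State that no CLD benefit will be claimed from the CLD row unless it is read together with this row and mortality. No composite for severe ROP is needed.

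The cost is one derived row from two outcomes already listed. The data spreadsheet is not shown, so date of death may have to be added if it is not collected.

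The downside is that the composite mixes death with morbidity and, when p is below 50%, responds more strongly to a pure death difference than CLD does. It is also less sensitive to a mortality difference than the planned mortality test: at 10% vs 20% deaths it reaches p < 0.05 in 6.0-7.4% of trials, against 14.5%. It should therefore be labelled a net-outcome measure and not a corrected CLD effect.
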